7.8.2 Prohibited concomitant treatments (medications and therapies)

Prohibited and/or restricted medications are summarized in [Table 7-1](#) and [Table 7-2](#).

Table 7-1: Prohibited or restricted medications

Drug class	Dose	Comments
Analgesics, including opioid analgesics (acetaminophen/paracetamol, etc)	Any dose	Any ad hoc use in the 24 hours prior to any study visit is prohibited. Stable doses of analgesics (including opioids) permitted.
TNF inhibitor: -infliximab -adalimumab -etanercept -golimumab -certolizumab pegol	Any dose	This applies to biosimilar versions of any TNF inhibitors.
Any non-TNF biologic medications	Any dose	Any exposure history is prohibited.
All other DMARDs	Any dose	Only permitted medications as per Section 7.8.1 .

DMARD=disease-modifying antirheumatic drug; TNF=tumor necrosis factor

Table 7-2: Additional prohibited psoriasis treatments

Drug class
Phototherapy
High potency topical steroid, vitamin D analogues, topical retinoids, keratolytics, coal tar, fumaric acid esters use except as detailed in Section 7.8.1
Systemic retinoids

Subjects who take prohibited medications may be withdrawn from study treatment but followed until the SFU Visit. The decision to withdraw a subject for taking prohibited medications should be made in consultation with the Medical Monitor.

Vaccines

Administration of live, attenuated vaccines is not allowed during the conduct of the study or for 20 weeks after the last dose of study drug. Administration of non-live, inactivated vaccines is allowed during the study at the discretion of the Investigator.

Live vaccinations include, but are not limited to, the following: anthrax vaccine, intranasal influenza vaccine, measles-mumps-rubella vaccine, polio live oral vaccine, smallpox vaccine, TB Bacillus Calmette-Guérin vaccine, typhoid live oral vaccine, varicella vaccine, and yellow fever vaccine.

7.9 Blinding

This is an open label study. All subjects' treatment assignments during the lead-in studies will remain blinded until final database lock of PA0008.

7.10 Randomization and numbering of subjects

This is an OLE study and no randomization will be performed. All subjects will receive bimekizumab 160mg Q4W sc.

Subjects will continue with the 5-digit subject numbers assigned by the interactive web or voice response system (IXRS) in the preceding study.

8 STUDY PROCEDURES BY VISIT

The schedule of study assessments (Table 5–1) provides a general overview of study assessments. A list of procedures to be completed at each visit is provided in the sections that follow.

- Visit windows of ± 7 days on either side of the scheduled dosing are permitted for all visits other than the SFU Visit (see below); however, the Investigator should try to keep the subjects on the original dosing schedule. The window of ± 7 days is relative to the first dose (PA0009 entry) and applicable for all subsequent visits. Changes to the dosing schedule outside of the 14-day window must be discussed with the Medical Monitor.
- The minimum time between doses should be no less than 21 days and no more than 35 days for Q4W dosing.
- For the SFU Visit (20 weeks after the last dose), the visit should occur no more than 3 days prior to the scheduled visit date and within 7 days after the scheduled visit date (-3 days/+7 days).

The Investigator should make efforts to maintain the original visit schedule. Changes to the dosing schedule outside of the allowed windows must be discussed with the Medical Monitor and may result in subject withdrawal.

8.1 Visit 1

The PA0009 entry assessments noted with an “*” will be obtained at the Week 48 Visit of PA0008 and do not need to be recorded on the eCRF for this study.

The following procedures or assessments will be completed prior to administration of IMP:

- Ensure that a separate ICF is completed by the subject for PA0009 (must be done prior to any PA0009 study procedures)
- Assessment of inclusion/exclusion criteria
- Record concomitant medications*
- Record AEs*
- eC-SSRS*
- HADS*

- Administer the Health Assessment Questionnaire—Disability Index (HAQ-DI)*
 - Administer the SF-36*
 - Administer the Patient’s Global Assessment of Disease Activity (PGADA)*
 - Administer the Patient’s Assessment of Arthritis Pain (PtAAP)*
 - Administer the PsAID-9*
 - Administer the TB questionnaire*
 - Measure vital signs (temperature, pulse, and blood pressure [BP])*
 - Measure body weight*
 - Perform a physical examination, including an evaluation for signs and symptoms of active TB and risk for exposure to TB*
 - Perform tender joint count (TJC)/swollen joint count (SJC)*
 - Determine BSA affected by PSO using the BSA palm method*
 - If the BSA affected by PSO is $\geq 3\%$ at Baseline of PA0008, determine the Psoriasis Area and Severity Index (PASI)*
 - Determine the MASES*
 - Determine the LDI*
 - Perform the Physician’s Global Assessment of Disease Activity (PhGADA)*
 - Perform an electrocardiogram (ECG)*
 - Collect samples for hematology/biochemistry/urine pregnancy*
 - Collect blood sample for CRP*
 - Collect blood sample for bimekizumab plasma concentrations and anti-bimekizumab antibody detection*
 - Perform an IGRA TB test if applicable
 - Record visit in the IXRS
 - Bimekizumab will be administered after all of the above assessments have been completed
- The following procedures or assessments will be completed following administration of IMP:
- Collect pulse and BP at 30 minutes and 1 hour after dosing

8.2 Week 4 (Visit 2) and Week 8 (Visit 3)

The following procedures or assessments will be completed prior to administration of IMP:

- Record concomitant medications
- Record AEs

- eC-SSRS
- Measure vital signs (temperature, pulse, and BP)
- Record visit in the IXRS
- Bimekizumab will be administered after all of the above assessments have been completed

The following procedures or assessments will be completed following administration of IMP:

- Collect pulse and BP once after dosing at any time

8.3 Week 12 (Visit 4), Week 24 (Visit 5), Week 36 (Visit 6), and Week 72 (Visit 9)

The following procedures or assessments will be completed prior to administration of IMP:

- Record concomitant medications
- Record AEs
- eC-SSRS
- HADS
- Administer the HAQ-DI
- Administer the SF-36
- Administer the PGADA
- Administer the PtAAP
- Administer the PsAID-9
- Administer the TB questionnaire
- Measure vital signs (temperature, pulse, and BP)
- Measure body weight
- Perform TJC/SJC
- Determine BSA affected by PSO using the BSA palm method
- If the BSA affected by PSO is $\geq 3\%$ at Baseline of PA0008, determine the PASI
- Determine the MASES
- Determine the LDI
- Perform the PhGADA
- Collect samples for hematology/biochemistry
- If there has been a delay in menses, perform a urine pregnancy test
- Collect blood sample for CRP

- Collect blood sample for bimekizumab plasma concentrations and anti bimekizumab antibody detection
- Record visit in the IXRS
- Bimekizumab will be administered after all of the above assessments have been completed

The following procedures or assessments will be completed following administration of IMP:

- Collect pulse and BP once after dosing at any time

8.4 Week 16, Week 20, Week 28, Week 32, Week 40, Week 44, Week 52, Week 56, Week 64, Week 68, Week 76, Week 80, Week 88, and Week 92

Subjects will be given the opportunity for self-administration of bimekizumab. Adverse events will be captured spontaneously if the subject decides to visit the site to receive the bimekizumab administration.

8.5 Week 48 (Visit 7) and Week 96 (Visit 11)

The following procedures or assessments will be completed prior to administration of IMP:

- Record concomitant medications
- Record AEs
- eC-SSRS
- HADS
- Administer the HAQ-DI
- Administer the SF-36
- Administer the PGADA
- Administer the PtAAP
- Administer the PsAID-9
- Administer the TB questionnaire
- Measure vital signs (temperature, pulse, and BP)
- Measure body weight
- Perform a physical examination, including an evaluation for signs and symptoms of active TB and risk for exposure to TB
- Perform TJC/SJC
- Determine BSA affected by PSO using the BSA palm method
- If the BSA affected by PSO is $\geq 3\%$ at Baseline of PA0008, determine the PASI

- Determine the MASES
- Determine the LDI
- Perform the PhGADA
- Perform an ECG
- Collect samples for hematology/biochemistry
- If there has been a delay in menses, perform a urine pregnancy test
- Collect blood sample for CRP
- Collect blood sample for bimekizumab plasma concentrations and anti bimekizumab antibody detection
- Perform an IGRA TB test
- Record visit in the IXRS
- Bimekizumab will be administered after all of the above assessments have been completed

The following procedures or assessments will be completed following administration of IMP:

- Collect pulse and BP once after dosing at any time

8.6 Week 60 (Visit 8) and Week 84 (Visit 10)

The following procedures or assessments will be completed prior to administration of IMP:

- Record concomitant medications
- Record AEs
- eC-SSRS
- HADS
- Administer the HAQ-DI
- Administer the SF-36
- Administer the PhGADA
- Administer the PtAAP
- Administer the PsAID-9
- Administer the TB questionnaire
- Measure vital signs (temperature, pulse, and BP)
- Measure body weight
- Perform TJC/SJC
- Determine BSA affected by PSO using the BSA palm method
- If the BSA affected by PSO is $\geq 3\%$ at Baseline of PA0008, determine the PASI

-
- Determine the LDI
 - Perform the PhGADA
 - Collect samples for hematology/biochemistry
 - If there has been a delay in menses, perform a urine pregnancy test
 - Collect blood sample for CRP
 - Record visit in the IXRS
 - Bimekizumab will be administered after all of the above assessments have been completed

The following procedures or assessments will be completed following administration of IMP:

- Collect pulse and BP once after dosing at any time

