10 ASSESSMENT OF EFFICACY

Several assessments must be completed in order to determine the ACR response. These include the TJC and SJC based on 78 and 76 joints, respectively, PGADA, PhGADA, PtAAP, HAQ-DI, and CRP. The methods for the component measures will be described first, followed by ACR response and assessments used in secondary and other efficacy variables.

The timing for all assessments is specified in the schedule of study assessments (Table 5-1).

10.1 78/76 joint evaluation for ACR response

The Principal Investigator, another delegated physician, or an appropriately qualified medical professional (based on local requirements) who has had documented training on how to perform

these assessments correctly assesses the following joints for tenderness: the distal interphalangeal, proximal interphalangeal and metacarpophalangeal joints of the hands, and metatarsophalangeal joints of the feet, the carpometacarpal and wrist joints (counted separately), the elbows, shoulders, acromioclavicular, sternoclavicular, hip, knee, talo-tibial, and midtarsal joints. All of these except for the hips are assessed for swelling.

Artificial and ankylosed joints, as well as missing joints (ie, amputated joints), are excluded from both tenderness and swelling assessments.

One dactylitic digit is to be counted as 1 swollen joint (instead of counting as 3 in the finger or 2 in the toe).

Table 10–1 summarizes the swelling and tenderness grading criteria.

Table 10–1: Swelling and tenderness grading

Grade	Swelling response (76)	Tenderness response (78)
0	None	Not tender
1	Detectable synovial thickening	Tenderness present

10.2 28 joint evaluation for determination of DAS28(CRP)

The following 28 joints will be used for calculation of the DAS28(CRP).

- Upper extremity (26)-bilateral shoulders, elbows, wrists (includes radiocarpal, and carpal and carpometacarpal bones considered as a single unit), metacarpophalangeal (MCP) I, II, III, IV, and V, thumb interphalangeals (IP), proximal interphalangeal (PIP) II, III, IV, and V
- Lower extremity (2)-knees

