### 2.2.2.3 Other efficacy variables

The other efficacy variables are listed below and will be evaluated at scheduled visits in accordance with the schedule of study assessments in [Table 2-1](#):

- ACR20, ACR50, and ACR70 response at each visit (PA0009 EV, Week 12, 24, 36, 48, 60, 72, 84, 96, 100, 104), relative to PA0008 Baseline.
  - ACR20, ACR50 and ACR70 response will also be reported at each post-PA0008 Baseline visit in PA0008 through to PA0009 Week 104 (PA0008 Week 2, 4, 8, 12, 16, 20, 24, 36 and PA0009 EV [PA0008 Week 48], Week 12, 24, 36, 48, 60, 72, 84, 96, 100, 104), for subjects who were responders at PA0008 Week 12. These are additional variables to those specified in the protocol and will be used to assess maintenance of response.
- PASI75, PASI90 and PASI100 response at each visit (PA0009 EV, Week 12, 24, 36, 48, 60, 72, 84, 96, 100, 104), relative to PA0008 Baseline.
  - PASI75, PASI90 and PASI100 response will also be reported at each post-PA0008 Baseline visit in PA0008 through to PA0009 Week 104 (PA0008 Week 2, 4, 8, 12, 24 and 36 and PA0009 EV [PA0008 Week 48], Week 12, 24, 36, 48, 60, 72, 84, 96, 100, 104), for subjects who were responders at PA0008 Week 12. These are additional variables to those specified in the protocol and will be used to assess maintenance of response.
  - BSA at each visit in PA0009 will also be reported. This is additional to the protocol and was added as an additional method of assessing response in order to provide information at visits where the PASI data may be missing.
- Minimal Disease Activity (MDA) at each visit (PA0009 EV, Week 12, 24, 36, 48, 72, 96, 104).
- Change from Baseline of PA0008 value in Disease Activity Score-28 based on C-reactive protein (DAS28[CRP]) at each visit (PA0009 EV, Week 12, 24, 36, 48, 60, 72, 84, 96, 100, 104).
- Change from Baseline of PA0008 in MASES at each visit (PA0009 EV, Week 12, 24, 36, 48, 72, 96, 104).
- Change from Baseline of PA0008 in the LDI at each visit (PA0009 EV, Week 12, 24, 36, 48, 60, 72, 84, 96, 100, 104).
- Change from Baseline of PA0008 in Psoriatic Arthritis Impact of Disease-9 (PsAID-9) at each visit (PA0009 EV, Week 12, 24, 36, 48, 60, 72, 84, 96, 100, 104).
- Change from Baseline of PA0008 in Short Form 36-item Health Survey (SF-36) at each visit (PA0009 EV, Week 12, 24, 36, 48, 60, 72, 84, 96, 100, 104).

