### 8.1.12 Disease Activity Score-28 based on C-reactive Protein

The components for DAS28(CRP) include the TJC and SJC based on 28 joints (see [Section 8.1.2](#)), CRP (mg/L), and the PGADA (mm). Any CRP values less than 0.16mg/L will be substituted as described in [Section 8.1.7](#) prior to calculating the DAS28(CRP) score.

If more than 50% of the planned joint assessments (ie, more than 14 assessments) are missing at a visit, then the TJC or SJC will be set to missing for that visit for the purposes of DAS28(CRP) calculation.

DAS28(CRP) is calculated as follows (where ‘ln’ represents the natural logarithm function):

$$DAS28(CRP) = 0.56 * \sqrt{TJC} + 0.28 * \sqrt{SJC} + 0.014 * PGADA + 0.36 * \ln(CRP + 1) + 0.96 \quad (15)$$

DAS28 (CRP) will be assessed using component assessments from the same analysis visit, ie, after applying any visit mapping as outlined in [Section 3.5](#).

If any individual component score is missing, the DAS28(CRP) will be missing.

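### Protocol Section 8.6 lists PhGADA twice and omits PGADA at Weeks 60 and 84, contradicting Table 5-1; a site that follows the list loses DAS28(CRP) and one ACR measure at those visits

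*Protocol*

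**What the plan says.** Section 8.6 of the protocol covers Week 60 (Visit 8) and Week 84 (Visit 10). Among the patient questionnaires, between the SF-36 and the pain scale, it has "Administer the PhGADA". Further down, after the joint, skin and dactylitis assessments, it has "Perform the PhGADA". The list does not mention PGADA. The Week 48 and Week 96 list in Section 8.5 has "Administer the PGADA" in the corresponding position. Sections 8.1, 8.3, 8.7 and 8.8 also include PGADA and name PhGADA once.

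Protocol Table 5-1 marks PGADA at Weeks 60 and 84, and SAP Table 2-1 repeats that row.

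On which text governs, the protocol points two ways. Section 8 describes Table 5-1 as an overview and adds: "A list of procedures to be completed at each visit is provided in the sections that follow". Section 10 says: "The timing for all assessments is specified in the schedule of study assessments". Section 4.3.2 likewise ties the other efficacy variables to Table 5-1.

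SAP Section 8.1.12 builds DAS28(CRP) from the 28-joint tender and swollen counts together with "CRP (mg/L), and the PGADA (mm"), and then states: "If any individual component score is missing, the DAS28(CRP) will be missing". SAP Section 2.2.2.3 plans the change in "DAS28[CRP]) at each visit (PA0009 EV, Week 12, 24, 36, 48, 60, 72, 84, 96, 100, 104"), so both affected visits are included. ACR20/50/70 are planned at the same visits, with PGADA as one of the five non-joint measures (SAP Section 8.1.8).

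**The concern.** Section 8.6 is an operative instruction, and a coordinator working from it would have no prompt to collect PGADA. The omission need not look like a slip. Compared with the list in Section 8.3, Section 8.6 correctly leaves out MASES and the drug-concentration and antibody samples, so a shorter list is expected at these visits.

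Three sets of results could be affected: DAS28(CRP), the summary of PGADA itself, and ACR response, both by visit and in the maintenance-of-response tables. Under nonresponder imputation (NRI) the ACR error runs one way only, so it could produce an artificial dip at Weeks 60 and 84. Week 60 also falls within the data snapshot described in SAP Section 4.3.

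For DAS28(CRP) and PGADA, SAP Table 4-2 plans multiple imputation (MI) only. No observed-case (OC) table would show such a gap.

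**Working it through.** The plan gives no figure to reproduce for this point. The check sets the texts side by side and then applies the SAP's missing-component rules with PGADA absent.

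**1. Where PGADA is listed**

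| Source | PGADA at Weeks 60 and 84? |
|---|---|
| Protocol Table 5-1 | Yes |
| SAP Table 2-1 | Yes |
| Protocol Section 8.6 | No; PhGADA twice |
| Protocol Sections 8.1, 8.3, 8.5, 8.7, 8.8 (other visits, for comparison) | PGADA and PhGADA once each |

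**2. Visits affected.** DAS28(CRP) is planned at entry and at Weeks 12, 24, 36, 48, 60, 72, 84, 96, 100 and 104. That is 11 visits, 10 of them after entry. Section 8.6 governs 2 of the 10. At a site following it, DAS28(CRP) can be derived from scheduled-visit data at 11 − 2 = 9 of the 11.

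**3. DAS28(CRP).** The formula in SAP Section 8.1.12 is 0.56·√TJC + 0.28·√SJC + 0.014·PGADA + 0.36·ln(CRP + 1) + 0.96. As a check that it is read correctly, setting the joint counts and PGADA to zero with CRP = 0.08 gives 0.36·ln(1.08) + 0.96 = 0.988, the minimum in SAP Table 4-1. The PGADA term runs from 0 to 0.014 × 100 = 1.4 points. With PGADA absent, the rule makes the whole score missing.

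**4. ACR.** The rule is improvement in both joint counts plus at least 3 of 5 other measures. Take both joint counts as improved and enumerate the 2⁵ = 32 patterns of improved or not improved on the five others.

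- Responders with all five measured: C(5,3) + C(5,4) + C(5,5) = 10 + 5 + 1 = 16.
- With PGADA absent, SAP Table 12-1 (four components present) gives a response if 3 or 4 of the remaining four improved. That is (4 + 1) × 2 = 10 patterns, all true responders.
- If exactly 2 of the four improved, the result cannot be determined and is coded as worst case. That is C(4,2) × 2 = 12 patterns.
- Six of those 12 have PGADA improved and are true responders (16 − 10 = 6). They become nonresponders under NRI. The other six are true nonresponders and stay so.
- All 12 are left out of the OC analysis.

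These are counts of patterns, not of patients. The proportion of patients affected cannot be derived from the documents.

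**5. Whether imputation repairs it.** If only some sites follow Section 8.6, MI can draw on observed PGADA and DAS28(CRP) from the rest. The MI sensitivity analysis for ACR would likewise impute PGADA. If nearly all sites followed it, the model would have almost no observed values at those visits to fit. SAP Section 4.2.1 then says only that last observation carried forward or OC summaries may be considered.

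**The case against.** The strongest reply is that every other source gives the right answer. For efficacy timing, Sections 4.3.2 and 10 point to Table 5-1 more specifically than Section 8 points away from it, and SAP Section 3.5 reports assessments according to the planned schedule. The entry is also recognisable as a slip. It sits among the patient questionnaires with the verb used for them, and read literally it has the investigator rate one scale twice before dosing. Section 10.4 asks for PhGADA to be made blind to PGADA, which presupposes that PGADA is collected. Patient-reported outcomes are captured on a site tablet (Section 12.3.1), which may have been set up from Table 5-1.

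Most of this stands. It makes loss less likely, and it shows that the omission was not a design choice. It does not remove the contradiction, because Section 8 still presents its visit lists as the procedures to complete, and the tablet's configuration is not documented.

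A reader might infer that DAS28(CRP) is missing for every subject at Weeks 60 and 84. The documents do not support that. It would require every site to follow Section 8.6 against Table 5-1. Even then, the early-termination assessments in Section 8.8 include PGADA, and SAP Section 3.5 can map them, or an unscheduled value in the window, to either visit.

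**Conclusion.** This is a real internal contradiction of low severity. Section 8.6 conflicts with Table 5-1, SAP Table 2-1 and the parallel visit lists, and the protocol does not clearly settle which governs.

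The effect is conditional on a site following Section 8.6 over the table. How many did is unknown and could be anything from none to all. At such a site, observed PGADA and DAS28(CRP) are missing at 2 of 10 post-entry efficacy visits, apart from mapped values. ACR is weakened rather than lost: with both joint counts improved, the misclassified responders under NRI are those who improved on PGADA plus exactly two other measures.

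The reach is limited. The primary variables are adverse events. All secondary efficacy variables are at Week 48, where Section 8.5 includes PGADA. Minimal Disease Activity, which also uses PGADA, is not planned at Weeks 60 or 84. What remains is the other by-visit efficacy summaries and the ACR maintenance-of-response tables at two visits, all descriptive. Reading this as evidence that data were lost would go beyond the documents.

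**What to change.** In protocol Section 8.6, replace "Administer the PhGADA" with "Administer the PGADA", so that the list agrees with Table 5-1, and send sites a short note. Check PGADA completeness at Weeks 60 and 84, by site, in the data already collected. If a site shows a systematic gap, say so beside the DAS28(CRP), PGADA and ACR summaries at those visits. The cost is a one-term correction, one site communication and one completeness listing; no analysis method changes.

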8.7 Week 100 (Visit 12)

The following procedures or assessments will be completed prior to administration of IMP:

- Record concomitant medications
- Record AEs
- eC-SSRS
- HADS
- Administer the HAQ-DI
- Administer the SF-36
- Administer the PGADA
- Administer the PtAAP
- Administer the PsAID-9
- Administer the TB questionnaire
- Measure vital signs (temperature, pulse, and BP)
- Measure body weight
- Perform TJC/SJC
- Determine BSA affected by PSO using the BSA palm method
- If the BSA affected by PSO is $\geq 3\%$ at Baseline of PA0008, determine the PASI
- Determine the LDI
- Perform the PhGADA
- Collect samples for hematology/biochemistry
- If there has been a delay in menses, perform a urine pregnancy test

- Collect blood sample for CRP
- Record visit in the IXRS
- Bimekizumab will be administered after all of the above assessments have been completed

The following procedures or assessments will be completed following administration of IMP:

- Collect pulse and BP once after dosing at any time

